# 6.2.2. Hospitalization

The frequency (annualized rate) of all-cause and cardiovascular-related hospitalizations during the study will be summarized descriptively separately for Cohort A and B. Cardiovascular relatedness will be based on an evaluation and clinical judgment of the MedDRA preferred terms.

# 6.2.3. Kansas City Cardiomyopathy Questionnaire

The KCCQ will be summarized by the following summary scores calculated using the guidelines established in the KCCQ scoring instructions from the developer:

Physical limitations	Self-efficacy
Symptom stability	Quality of life
Symptom frequency	Social limitation
Symptom burden	Overall summary score
Total symptom score	Clinical summary score

For Cohort A, the overall, domain, and clinical summary scores will be evaluated as a change from baseline at each visit using a MMRM (repeated measures mixed model) with an unstructured covariance matrix (or as appropriate) with center and subject-within-center as a random effects and treatment (tafamidis/tafamidis and placebo/tafamidis), visit, TTR genotype (variant and wild- type), and visit-by-treatment interaction, as fixed effects and baseline score as covariate. *Data will also be summarized by each scheduled assessment*.

As defined in Section 3.4, the baseline for Study B3461028 will be used as the baseline for all KCCQ based analyses. All visits from Study B3461028 will also be included in the repeated measures model described above.

For Cohort B, descriptive statistics for change from baseline at each post-baseline visit will be provided.

# 6.2.4. New York Heart Association

For Cohorts A and B, subjects will be evaluated using the New York Heart Association (NYHA) classification. Descriptive statistics (frequency) will be presented by clinic visit for each classification: Class I, Class II, Class III, and Class IV. The number and percentage of subjects who improved, worsened, or with no change from baseline will also be presented at each visit via a shift table.

# 6.2.5. Body Mass Index/modified Body Mass Index

For Cohorts A and B, BMI and mBMI values at each visit and change from baseline will be presented in summary tables and data listings. Descriptive statistics will be provided by visit.

# 6.2.6. NT-proBNP and Troponin I

For Cohort A, as defined in Section 3.4, the baseline for Study B3461028 will be used as the baseline for all NT-proBNP and Troponin I based analyses. Change from baseline for all visits, including the visits from Study B3461028 will be summarized descriptively for NT-proBNP and Troponin I by treatment group (tafamidis/tafamidis and placebo/tafamidis).

For Cohort B, descriptive statistics for change from baseline at each post-baseline visit will be provided for NT-proBNP and Troponin I.

#### 6.3. Subset Analyses

All Cohort A and Cohort B analyses will be repeated by genotype (wild type and variant) separately.

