# 5.1. Hypotheses and Decision Rules

The primary objective of the study is to obtain additional, long term, safety data for tafamidis in subjects with transthyretin cardiomyopathy (ATTR-CM) and to provide investigational product, tafamidis, to ATTR-CM subjects who complete 30 months of blinded treatment on protocol B3461028 (Cohort A) and to Subjects diagnosed with ATTR-CM who have not previously participated in Study B3461028 (Cohort B). Therefore, only limited hypothesis testing ie, mortality and change from baseline in KCCQ for Cohort A subjects will be performed. All hypothesis testing will be conducted using two-sided tests with alpha = 0.05 level of significance. Since the primary objective of the study is to collect safety information, no multiplicity adjustment will be done. No hypothesis testing will be done on Cohort B subjects.

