# 6. ANALYSES AND SUMMARIES

# 6.1. Primary Endpoint(s)

#### 6.1.1. All-cause Mortality

For Cohort A subjects, time to all-cause mortality will be calculated from Day 1 of the Study B3461028 based on the "Combined Mortality Analysis Set" as defined in Section 4.4. All-cause mortality will be analyzed using SAS Proc Lifetest; p-values will be from the log-rank test. Kaplan-Meier survival curves for each treatment group along with median survival times (if applicable) will be presented comparing tafamidis/tafamidis group with placebo/tafamidis group.

All-cause mortality will also be analyzed using Cox proportional hazards model with treatment, NYHA baseline classification, and TTR genotype (variant and wild-type) as factors. Subjects who discontinue for transplantation (ie, heart transplantation and combined heart and liver transplantation) or for implantation of a cardiac mechanical assist device, will be handled in the same manner as death. Data from subjects who drop out for a liver-only transplantation will be handled in the same manner as the data from all other censored subjects.

To examine the potential effect of including heart transplantation or cardiac mechanical assist device as "deaths" in the all-cause mortality analysis, a sensitivity analysis will be performed treating all transplantation or cardiac mechanical assist device in the same manner as any other censored observation.

For Cohort B, since subjects in this Cohort will all be administered the same dose, only overall descriptive statistics will be provided. Kaplan-Meier survival curve along with median survival time (if applicable) will be presented.

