#### 9. APPENDICES

#### **Appendix 1. SUMMARY OF ANALYSES**

#### **Summary of Proposed Analyses**

End Point or Assessment	Overall ##	Wild-type vs Variant
All cause mortality.#	Х	Х
Cardiovascular related mortality.#	Х	х
Frequency of all cause hospitalization.	х	X
Frequency of cardiovascular related hospitalization (including heart failure, arrhythmia, myocardial infarction, stroke and other cardiovascular related events).	x	X
Change from baseline at each visit in Kansas City Cardiomyopathy Questionnaire Overall Score, domain scores (Physical limitation, Symptom stability, Symptom frequency, Symptom burden, Total symptom, Self efficacy, Social limitation, and Quality of life) and clinical summary score #	X	х
New York Heart Association classification at each visit.	X	X
Change from baseline in Body Mass Index/modified Body Mass Index at each visit.	X	X
Change from baseline in NT-proBNP at each	х	х
Change from baseline in Troponin I at each visit.#	х	х
Assessment of physical examinations, use of concomitant medications, electrocardiograms (ECGs), clinical laboratory testing, vital signs at each visit.	X	x

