#### **Appendix 2. STATISTICAL METHODOLOGY DETAILS**

Sample SAS code for time to event analysis is given below.

PROC LIFETEST DATA=xxx PLOTS=(s) graphics; TIME dur \*status(0); STRATA trt; RUN;

PROC PHREG DATA=xxx; MODEL dur\*status(0)=trt genotype NYHAbase/ ties=EXACT; RUN;

Sample SAS code to fit the mixed model repeated measures is given below. The response variable Y is the change from baseline at the study visits.

PROC MIXED DATA=xxx METHOD=REML EMPIRICAL; CLASS pid center trt visit genotype; MODEL y= ybase trt visit genotype trt \*visit; RANDOM int/SUBJECT=center; REPEATED visit /SUBJECT= pid (center) r type=UN; RUN;

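### The Cohort A mortality and KCCQ tests are repeated within each genotype, but no planned analysis estimates whether the treatment effect differs by genotype

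*SAP*

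**What the plan says.** SAP 6.3 is one sentence: "All Cohort A and Cohort B analyses will be repeated by genotype (wild type and variant) separately". The Appendix 1 table of analyses ticks every listed endpoint in a column headed "Wild-type vs Variant".

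SAP 5.1 settles which of these repeats carry a test: "only limited hypothesis testing ie, mortality and change from baseline in KCCQ for Cohort A subjects will be performed". It continues, "All hypothesis testing will be conducted using two-sided tests with alpha = 0.05 level of significance", and adds that "no multiplicity adjustment will be done". For the other cohort, "No hypothesis testing will be done on Cohort B subjects". The tested repeats are therefore Cohort A all-cause mortality, cardiovascular-related mortality (which SAP 6.2.1 analyses in the same way) and the ten KCCQ scores in SAP 6.2.3.

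The models are these:
- **Mortality, SAP 6.1.1:** "All-cause mortality will also be analyzed using Cox proportional hazards model with treatment, NYHA baseline classification, and TTR genotype (variant and wild-type) as factors". The Appendix 2 code agrees: "trt genotype NYHAbase/ ties=EXACT". Protocol 9.3.1 also lists genotype as a factor only.
- **KCCQ, SAP 6.2.3 and Appendix 2:** genotype is a main effect, and the only interaction is treatment by visit.

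**The concern.** Two separate tests, one per genotype, do not test whether the genotypes differ. A p-value below 0.05 in one subset and above it in the other is an expected result when the effect is identical in both, especially if one subset is much smaller. The smaller genotype then tends to look unresponsive because it has fewer events.

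Genotype is a prominent factor here. It stratifies Cohort A treatment assignment (protocol 5.1.1), it is a factor in both models, and it is the only subset that SAP 6.3 names. Protocol 1.1 covers both variant and wild-type disease, and SAP 5 allows interim results to be reported to the scientific community. A genotype table with one significant and one non-significant row could be misread, and the plan provides no estimate that would correct the reading.

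**Working it through.** **Is there an interaction term anywhere?** The places where one could appear are SAP 6.1.1, 6.2.1, 6.2.3, 6.3, Appendix 1, both code blocks in Appendix 2, and protocol 9.2.3 and 9.3.1. The only interaction in any of them is treatment by visit in the MMRM. No rule says how the two subset p-values are to be read against each other.

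**How often would the subset p-values disagree if the effect is the same?** The plan has no figure to reproduce. Protocol 9.1 gives no formal sample size calculation, and neither document gives an expected number of deaths, a hazard ratio or the genotype split.

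Inputs:
- From SAP 5.1: two-sided alpha 0.05, so the critical value is 1.96.
- Assumed: D = 180, 250 or 300 deaths in total; a share s = 20%, 25% or 30% of them in the smaller genotype; 60:40 allocation; a common HR of 0.60, 0.70, 0.80 or 0.90.

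Formulas, with d the deaths in a subset:
- Subset power = Φ(|ln HR| × √(d × 0.6 × 0.4) − 1.96)
- P(exactly one subset significant) = a(1 − b) + b(1 − a), where a and b are the two subset powers. The subsets are disjoint, so they are treated as independent.

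Worked case, HR 0.70, D = 250, s = 25%:
- Larger subset: d = 187.5; √(187.5 × 0.24) = 6.708; 0.3567 × 6.708 − 1.96 = 0.433; a = 0.667.
- Smaller subset: d = 62.5; √(62.5 × 0.24) = 3.873; 0.3567 × 3.873 − 1.96 = −0.579; b = 0.281.
- Larger only: 0.667 × 0.719 = 0.480. Smaller only: 0.281 × 0.333 = 0.094. Exactly one: about 0.573.

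Range over all nine combinations of D and s:

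| Common HR | Larger subset p<0.05 | Smaller subset p<0.05 | Larger only | Smaller only | Exactly one |
|---|---|---|---|---|---|
| 0.60 | 80.2-97.2% | 32.3-66.1% | 32.3-57.6% | 1.4-8.9% | 35.5-62.4% |
| 0.70 | 50.1-77.2% | 18.1-38.1% | 37.6-56.2% | 6.2-12.5% | 50.0-62.4% |
| 0.80 | 23.2-39.5% | 9.6-17.8% | 20.3-34.3% | 7.1-11.5% | 29.8-42.3% |
| 0.90 | 8.4-12.3% | 4.9-7.1% | 7.9-11.6% | 4.5-6.3% | 13.1-16.8% |

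With wider assumptions (150-300 deaths, HR 0.60-0.80, 50-67% of subjects in one arm, and 50-80% of the deaths in one genotype) the last column runs from 21% to 63%. With no effect in either genotype it is 2 × 0.05 × 0.95 = 9.5% per endpoint.

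**What would an interaction test do?** With identical effects, a two-sided 0.05 test of the difference between the subset estimates signals a difference in 5% of trials; simulation gave 4.96-5.03%. Among simulated trials with disagreeing subset p-values (overall power 80% or 90%, shares of 50% or 75%), only about 7-10% also had a significant interaction.

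**How precise would the interaction be?** In the worked case the standard error of the log ratio of hazard ratios is √(1/15 + 1/45) = 0.298. The 95% CI therefore extends by a factor of exp(1.96 × 0.298) = 1.79 either side of the estimate, which is wide.

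**The case against.** The strongest reply is that this is a descriptive safety extension. Effect modification by genotype is not an objective, and SAP 5.1 limits testing and explains why it does not adjust for multiplicity. Showing results within a stratification factor is a common consistency display. That holds, and it makes this a minor point. It does not remove it, because SAP 5.1 designates mortality and KCCQ for formal testing and SAP 6.3 makes no exception for their repeats.

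Three stronger readings are tempting, and the documents do not support them.
- A reader might infer from the heading "Wild-type vs Variant" that Appendix 1 promises a contrast the plan never delivers. The footnote explains that the neighbouring column means the analysis is not a subgroup analysis, and the genotype column is also ticked for purely descriptive items. It simply marks the subgroup repeats.
- A reader might infer that the SAP means to conclude that a genotype difference exists from unequal p-values. It never says so.
- A reader might infer that the study cannot address the question. The subsets are disjoint, so a difference can be calculated from the two estimates and their standard errors. What is missing is a pre-specified analysis.

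The size of the problem also depends on the assumed hazard ratio. An HR of 0.70 gives the highest minimum of the four values tried, and near the null disagreement is much less common. No figure was calculated for KCCQ from its own inputs.

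**Conclusion.** The point holds as a low-cost improvement. The tested Cohort A analyses are repeated by genotype, and no analysis in either document estimates a treatment-by-genotype difference. With a moderate common effect on mortality (HR 0.60-0.80), the subset p-values would disagree in about 30-62% of trials, against 5% false signals from an interaction test. At HR 0.90 they would disagree in 13-17%. At the assumed splits most of the disagreement runs one way, with the larger subset significant and the smaller one not, which reflects size and not biology.

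The percentages rest on assumed deaths, genotype share, allocation and hazard ratio. The structural finding rests on none of these. It applies only to Cohort A mortality and KCCQ, since Cohort B and the other endpoints are descriptive.

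**What to change.** Leave the main Cox model and MMRM as they are, and add supplementary models to SAP 6.3 for Cohort A:
- **All-cause and cardiovascular-related mortality:** the Cox model plus a treatment-by-genotype term.
- **KCCQ:** the MMRM plus treatment-by-genotype, genotype-by-visit and treatment-by-genotype-by-visit terms. The endpoint is change at each visit, and a single two-way term would force the genotype difference to be constant over visits.

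Report the interaction estimates with 95% CIs and the genotype-specific effects with CIs. Omit the subset p-values, or label them descriptive, for both mortality endpoints and all KCCQ scores. State that the genotype term, which is constant within a subset, is left out of any separate-subset run.

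The cost is SAP wording and a few extra model runs, with no new data. Keeping the models supplementary matters. Adding the interaction to the main Cox model would turn its treatment coefficient into the effect in the reference genotype. That would alter the analysis of a primary endpoint, and protocol section 9 and SAP section 2 require major changes of that kind to be reflected in a protocol amendment. The downside is low power: the interaction should be read from its interval, and a non-significant result would not show that the effects are equal.

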# 6.4. Baseline and Other Summaries and Analyses

Subjects disposition, demographics, treatment exposure, and concomitant medications will be summarized descriptively for both Cohort A and Cohort B separately.

# 6.5. Safety Summaries (including other endpoints)

All safety endpoints listed in this section will be analyzed descriptively for Cohorts A and B separately.

# 6.5.1. Adverse Events

All AE data collected on the CRF will be presented in summary tables and data listings.

All adverse events that are observed from the time of first dosing with study medication until the treatment end date will be included in the safety analysis. Adverse events that occurred during treatment will be reported separately if the event occurred prior to randomization.

The effective duration of treatment is determined by the lag time. Any event occurring within the lag time, whether this occurs during a break in treatment or at the end of treatment, is attributed to the corresponding treatment period. A lag of 28 days will be used for this study. Treatment emergence is defined in Section 3.5.1.

All adverse events will be coded according to the Medical Dictionary for Regulatory Activities (MedDRA) and will be summarized by treatment group. The incidence of treatment-emergent adverse events will be tabulated by treatment group and by system organ class. The incidence of treatment-emergent adverse events will be displayed by severity and attribution. In addition, the incidence of serious adverse events and adverse events that cause withdrawal will be tabulated. All adverse events will be listed. All subjects in both Cohort A and B will be permitted one open label dose-reduction to 20 mg. All adverse events that led to temporary dose discontinuation or dose reduction will be summarized.

For Cohort A subjects who ended participation in B3461045 study without achieving the completion criteria of sustainable access to tafamidis by prescription, and allowed to return to the study and continue participation until they reach protocol defined study completion, adverse events that occurred between the time a subject ended the participation and subsequently returned will be collected and evaluated for treatment-emergence in the same manner as adverse events that occurred during the study participation.

Given that in B3461045 all subjects will be receiving active treatment, 3-tier analysis will not be performed on the adverse events.

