1. INTRODUCTION

1.1. Indication

Pfizer is developing tafamidis, an oral small molecule, for the treatment of transthyretin amyloid diseases. Tafamidis has been demonstrated to stabilize transthyretin and is being developed for the treatment of ATTR-CM in patients with variant or wild-type TTR to reduce the combination of all-cause mortality and cardiovascular-related hospitalization.

Tafamidis is currently approved in the United States for treatment of cardiomyopathy of wild-type or hereditary transthyretin-mediated amyloidosis (ATTR-CM) in adults to reduce cardiovascular mortality and cardiovascular-related hospitalization. Tafamidis is also approved for the treatment of ATTR-CM in Japan.

Tafamidis is currently approved for treatment of ATTR-PN in 41 countries and is commercially available in the following 26 countries: Argentina, Austria, Belgium, Brazil, Bulgaria, Czech Republic, Denmark, Finland, France, Germany, Greece, Hungary, Israel, Italy, Japan, Lichtenstein, Luxembourg, Netherlands, Norway, Poland, Portugal, Romania, Slovenia, Spain, Sweden and United Kingdom.

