Study B3461028 was a 30-month, Phase 3, double-blind, placebo-controlled, randomized, parallel-group trial designed to evaluate the efficacy, safety and tolerability of oral dosing of tafamidis meglumine 20 mg or 80 mg in comparison to placebo in subjects diagnosed with transthyretin cardiomyopathy and heart failure. The study enrolled 441 male and female subjects aged 18 to 90 years, with ATTR-CM due to either variant, or wild type TTR from sites in North and South America, the European Union, and Japan. The primary analysis included all-cause mortality and the frequency of cardiovascular-related hospitalizations and demonstrated a statistically significant reduction in the combination of all-cause mortality and frequency of cardiovascular-related hospitalizations compared to placebo. The preliminary safety data showed that tafamidis was generally well tolerated in this subject population and no new safety signals were identified.

The B3461045 protocol was designed as a long-term extension safety study for subjects who have completed 30 months of blinded treatment in Study B3461028. Given the positive results of the B3461028 study and the favorable benefit to risk profile there was a justification to provide patients with an option for early access to tafamidis. Consequently, the B3461045 study protocol was amended to include an additional cohort of patients with ATTR-CM who did not previously participate in the B3461028 parent study (Cohort B). The purpose of the additional cohort is to provide these patients early access to tafamidis, until local availability by prescription for the ATTR-CM indication. Additionally, a new formulation which is bioequivalent to tafamidis meglumine 80 mg has been developed and is presented as tafamidis 61 mg (as the free acid). This formulation, where available, will replace the tafamidis meglumine 80 mg dose after protocol amendment 3.

The current protocol describes a long-term safety extension study for subjects diagnosed with ATTR-CM who completed 30 months of participation in Study B3461028 (Cohort A) and subjects diagnosed with ATTR-CM who have not previously participated in the B3461028 (Cohort B).

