# 2.2. Study Design

This is a Phase 3, open-label long-term extension safety study designed to obtain additional safety data for tafamidis meglumine 20 mg and 80 mg (or tafamidis 61 mg where available), and to continue to provide enrolled subjects with tafamidis for up to 60 months, or until subject has access to tafamidis for ATTR-CM via prescription, whichever occurs first. The study will also end before 60 months if the sponsor discontinues the study. Subjects withdrawn from the study due to commercial access to prescription tafamidis in their

DMB02-GSOP-RF02 3.0 STATISTICAL ANALYSIS PLAN TEMPLATE 30-Jun-2015 PFIZER CONFIDENTIAL Page 9 TMF Doc ID: 98.03 respective countries will be considered study completers. The decision to withdraw subjects for transition to commercial tafamidis will be made by the sponsor.

Eligible study participants will be enrolled in 2 Cohorts:

- Cohort A Subjects diagnosed with ATTR-CM who completed 30 months of participation in Study B3461028.
- Cohort B Subjects diagnosed with ATTR-CM who have not previously participated in Study B3461028.

Cohort A subjects receiving tafamidis meglumine 20 mg or 80 mg will be assigned to tafamidis 61 mg, once daily, in addition to standard of care (eg, diuretics), for up to 60 months. Subjects will be assigned to tafamidis meglumine 80 mg in regions where 61 mg tafamidis is unavailable.

At enrollment, subjects in Cohort B will be assigned to open label 61 mg tafamidis once daily, in addition to standard of care (eg, diuretics), for up to 60 months. One dose reduction to 20 mg tafamidis meglumine will be permitted for adverse events related to tolerability. Subjects will be assigned to 80 mg tafamidis meglumine in regions where 61 mg tafamidis is unavailable.

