# **3. ENDPOINTS AND BASELINE VARIABLES: DEFINITIONS AND CONVENTIONS**

# 3.1. Primary Endpoint(s)

Safety as measured by:

- All-cause mortality.
- Incidence of treatment-emergent adverse events.

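### TEAE incidence is a primary endpoint, but SAP 6.5.1 gives it no person-time measure although length of exposure varies by design up to 60 months

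*SAP*

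**What the plan says.** SAP 3.1 lists "Incidence of treatment-emergent adverse events" as a primary endpoint next to all-cause mortality. SAP 6.5.1 then states: "The incidence of treatment-emergent adverse events will be tabulated by treatment group and by system organ class". It adds displays by severity and attribution, and tables of SAEs, AEs causing withdrawal, and AEs leading to temporary discontinuation or dose reduction. Protocol 9.3.2 uses the same incidence wording. Neither document gives a rate per patient-year, a person-time denominator or a time-to-first-event analysis for AEs. SAP Appendix 1 does not list TEAEs.

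Length of exposure is left open. Under SAP 2.2, treatment lasts up to 60 months or until prescription access, and the study can be ended earlier. "The decision to withdraw subjects for transition to commercial tafamidis will be made by the sponsor", and subjects who move in their "respective countries will be considered study completers". Protocol Appendix 4.1 ends the study in France and Germany 24 months after local approval unless it is continued. Protocol 1.2 records that "the B3461045 study protocol was amended to include an additional cohort of patients with ATTR-CM" and that "The purpose of the additional cohort is to provide these patients early access to tafamidis, until local availability by prescription for the ATTR-CM indication".

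Elsewhere the SAP does allow for time. Hospitalization gets an annualized rate (6.2.2) and mortality gets Kaplan-Meier and Cox analyses (6.1.1). Treatment exposure is summarized by cohort (6.4).

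**The concern.** The percentage of subjects with an event mixes how often events occur with how long subjects were watched. When follow-up ranges from a few months to five years, and an administrative exit counts as completion, one percentage has no clear time reference. Two groups with the same underlying event rate will show different percentages if their exposure differs. The first primary objective is long-term safety data, so this affects the main descriptive result of the study.

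The exposure summary in SAP 6.4 does not close the gap. Total exposure does not give the time at risk up to the first event for each AE row. For common events, which occur early, the two denominators differ materially.

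**Working it through.** The documents give no AE rate, exposure distribution or sample-size figure for TEAEs, so there is no planned number to reproduce. Only the 60-month ceiling and the 28-day lag come from the documents. Every event rate, exit rate and gap length below is an assumption, used to show scale.

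**1. Same rate, different uniform exposure.** Crude incidence = 1 − exp(−r·t). For example, r = 0.1 and t = 2 years gives 1 − exp(−0.2) = 18.1%.

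| Rate per year | 6 months | 24 months | 60 months |
|---|---|---|---|
| 0.1 | 4.9% | 18.1% | 39.3% |
| 0.3 | 13.9% | 45.1% | 77.7% |
| 1.0 | 39.3% | 86.5% | 99.3% |

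**2. The reverse.** Rate = −ln(1 − p)/t. A crude 20% means −ln(0.8)/1 = 22.3 per 100 patient-years if everyone is followed for 12 months, 11.2 for 24 months and 4.5 for 60 months. That is a five-fold range for one percentage.

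**3. Variable exposure, two groups with the same event rate.** Assume a constant exit rate d and a cap at 5 years. Mean exposure = (1 − exp(−5d))/d. Crude incidence = r/(r + d) × (1 − exp(−5(r + d))).
- d = 0.15: mean (1 − 0.4724)/0.15 = 3.52 years, or 42.2 months.
- d = 0.20: mean (1 − 0.3679)/0.20 = 3.16 years, or 37.9 months.
- At r = 0.1: 0.4 × (1 − exp(−1.25)) = 28.5% versus 0.333 × (1 − exp(−1.5)) = 25.9%.
- At r = 0.3: 59.6% versus 55.1%. At r = 1.0: 86.7% versus 83.1%.

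The gaps are 2.6, 4.5 and 3.6 points. This is the sort of difference that might arise between the two Cohort A groups if they leave at slightly different rates.

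**4. Limit of a single rate.** Under a constant hazard, first events divided by person-time return the same rate whatever the exit pattern, because that is what the model assumes. Suppose instead that the hazard is 0.3 per year in year 1 and 0.1 per year afterwards. With d = 0.15, expected first events are 0.403 over 2.418 patient-years, or 16.7 per 100. With d = 0.60 they are 0.252 over 1.205, or 20.9 per 100. The underlying risk is the same, so the rate reduces the exposure effect without removing it.

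**5. Returning Cohort A subjects.** SAP 5.3 and 6.5.1 evaluate AEs from the period between leaving and returning for treatment emergence. SAP 3.5.1 makes a new event treatment-emergent only within the effective duration, which carries a 28-day lag. If a rate counted events beyond the lag but not the matching time, it would be too high. Assume two 18-month spells on drug, the gap off drug, and the same event rate throughout. Let a = 18 months + 28 days = 1.577 years and g = gap − 28 days. The overstatement of the first-event rate is

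[1 − exp(−r(2a + g))] / {[1 − exp(−ra)] × [1 + exp(−r(a + g))]} − 1.

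For a 12-month gap, g = 0.923. At r = 0.3 this is 0.7057/(0.3769 × 1.4724) − 1 = 27.2%. At r = 0.1 it is 29.0% and at r = 1.0 it is 14.5%. This applies to a returner's contribution, not to the whole cohort. It arises only if a rate is introduced without a matched window.

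**The case against.** The strongest reply is that the plan rests nothing on these percentages. SAP 6.5 describes the cohorts separately, SAP 5.1 limits testing to mortality and KCCQ in Cohort A, and 6.5.1 declines a 3-tier AE analysis. The only AE groups set side by side are the two in Cohort A. Exposure is summarized, all AEs are listed, and a rate could be produced later from the same data. This stands and limits the weight of the point. It does not remove the difficulty of reading a primary-endpoint percentage over mixed follow-up, and a rate chosen after the data are seen is weaker than one stated in advance.

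A reader might infer that Cohort B has much shorter exposure than Cohort A, because it was added later and "Tafamidis is currently approved in the United States for treatment of cardiomyopathy" and "Tafamidis is also approved for the treatment of ATTR-CM in Japan", both Cohort B countries in Protocol Appendix 5. The documents do not establish this. The parent study also had sites in North America and Japan, the prescription exit applies to all subjects, and exposure by cohort is not reported. A contrast such as 42 versus 19 months (d = 0.15 versus 0.60), which would give 28.5% versus 13.9% at 0.1 per year, is only a choice of exit rates.

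A reader might also infer that a patient-year rate would make Cohorts A and B comparable. It would not. Cohort A subjects had survived and completed 30 months in the parent study, many on tafamidis, and events already seen there count as new only if they worsen. Cohort B comes from outside that study.

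**Conclusion.** The omission is real: a primary safety endpoint has no measure that allows for time, in a study where time on treatment varies by design. The consequence is limited interpretability of a descriptive result. It is not a biased test or a wrong decision rule. The size depends on exposure that the documents do not report. It is large if follow-up within a cohort spans months to years (4.9% to 39.3% at an assumed 0.1 per year), and probably about 3 to 5 points between the Cohort A groups if their mean exposure is close. All of this rests on assumed constant rates. The change is inexpensive and should be made, as a supplement to the percentages and not as a replacement.

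**What to change.** In SAP 6.5.1, beside each percentage for TEAEs, SAEs and AEs leading to withdrawal, add the number of subjects with a first event per 100 patient-years at risk, by cohort and treatment group. Keep it descriptive, with no test.

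- Denominator: person-time to the first event or to the end of risk, computed for each AE row.
- Window: count events and time over the same period, the SAP's effective duration of treatment (time on drug plus the 28-day lag after each stop).
- Returning subjects: leave off-drug time, and events beyond the lag, out of the rate, but still list those events. SAP 5.3 does not say whether any of them took prescribed tafamidis while away, so state how such time is classified.
- Wording: SAP 6.5.1 cuts AE inclusion off at the end of treatment in one paragraph and applies the lag in the next, while Protocol 9.3.2 runs to the end of participation. Align these with the chosen window.

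The cost is SAP text and programming of person-time for each AE row, repeated by genotype under SAP 6.3. No new data and no protocol change to the endpoint are needed. The downside is that a single rate assumes a roughly constant hazard. A table footnote should say so, and should add that the rate does not by itself support comparing Cohort A with Cohort B.
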